### 4.2. Device Classification and Rationale

In the United States (US), the SenoClaire® - GE Breast Tomosynthesis (DBT) is considered to be Class III, as defined by the US FDA CFR 1020.30-33. FFDM devices without tomosynthesis or computed tomography breast imaging devices are considered to be Class II, as defined by the US FDA 21 CFR 892.1715. In Europe, the SenoClaire® - GE Breast Tomosynthesis (DBT) is considered to be Class IIb as defined by the French National Agency for the Safety of Medicine and Health Products regulations in accordance with the European Medial Directive 93/42/EEC.

The IDI MammoWorkstation is a Class II medical device under 21 CFR 892.2050 Picture Archiving and Communications Systems (product Code LLZ) and Class IIa (special controls) in Europe.

### 4.3. Device Issuance and Replacement

SenoClaire® - GE Breast Tomosynthesis (DBT), FFDM, and IDI MammoWorkstation devices used in this study are commercially available. Unique identifying information (e.g. model, serial number, etc.) of each device used in this study will be recorded.

Ancillary equipment, including safety equipment such as protective vests, and surgical equipment necessary for biopsy(ies) procedure(s) will be used in this study according to the standard of care at the investigational site. These devices will be owned and maintained by the investigational site.

Sites will be encouraged to use equipment owned by the site, if available. For sites that do not own required mammography equipment (DBT, FFDM, and/or IDI MammoWorkstation) or component software versions necessary to complete study procedures, the Sponsor may provide devices for study use.

#### **4.3.1. Maintenance of Research Devices**

Devices used in this study will be maintained, calibrated, and ensured to be functioning correctly during the study, in accordance with applicable site policy and state and federal requirements. The Site Principal Investigator (PI) should inform the Sponsor of any known or anticipated issues with device functionality or availability that could impact the conduct or outcomes of this research study.

#### **4.3.2. Concurrent Use of Research Devices**

The DBT and FFDM devices used in this study are commercially available, multiple-use devices. Devices owned by the site may be used concurrently in this research and for standard of care procedures outside of this study. Devices provided to the site by GE shall be limited to use only for this protocol. The site is responsible for completing routine care, such as prevention of cross-contamination, between procedures that could impact study subjects.

#### **4.3.3. Device Software and Configuration Management**

The most current commercial configuration and software version for SenoClaire® - GE Breast Tomosynthesis (DBT) will be used during this study, and the site(s) should use an IDI MammoWorkstation with software version 4.7 MR2 or higher (capable of viewing V-Preview images). In the event of commercial release of software versions or configuration changes that will be implemented on devices used in this study, changes shall not increase risk classification of the study. The Site Principal Investigator (PI) is responsible for notifying the Sponsor of any current or planned software or configuration changes, including the date of implementation on a per-device basis. The Sponsor may, at its discretion or upon site request, require additional training or quality control procedures (e.g. calibration or other routine engineering maintenance activities) following software or configuration changes.

#### **4.4. Disposition of the Device/Product**

Devices and associated accessories, provided to the site for the purposes of this clinical trial, will be collected at the end of the study and returned to GE Healthcare.

## 5. OBJECTIVES OF RESEARCH STUDY

### 5.1. Hypothesis

No statistical hypothesis is tested in this data collection study. The sample size for screening mammography subjects in this study is determined to provide sufficient accrual of non-cancer cases for a subsequent statistically powered analysis as part of a separate protocol (ADAPT-BIE).

### 5.2. Study Objectives

#### 5.2.1. Primary Objective(s)

The aim of this recruitment plan (ADAPT-SCR) is to collect image and other data on both digital breast tomosynthesis (DBT) and full-field digital mammography (FFDM) from asymptomatic women undergoing screening mammography. These data will be included in a subsequent and prospectively planned pooled analysis described in a separate protocol (ADAPT-BIE) examining superiority of DBT to FFDM for breast cancer diagnosis and other clinical performance measures

#### 5.2.2. Characteristic Objectives

An exploratory aim is to describe cancer and non-cancer cases identified in this accrual study based on histology findings and lesion type.

### 5.3. Study Endpoints

#### 5.3.1. Primary endpoints

The primary endpoint will be the site's diagnosis of cancer status (positive or negative/benign) for each subject based on DBT and FFDM at baseline (0 months) and 10-16 months, and/or (if clinically indicated) histology and surgical findings. Histologic concordance with imaging will be assessed for benign lesions, when applicable, and DBT and FFDM image sets will be assessed using BI-RADS® scores.

#### 5.3.2. Characteristic Endpoints

Characteristic endpoints for all subjects will include histology findings and size, lesion type, and other lesion characteristics based on image appearance. Technical factors of image data collected from subjects, such as information related to radiation dose, may be extracted and analyzed by the Sponsor for the purposes of this study.

#### 5.3.3. Safety endpoint

Device-related adverse events (AEs), serious adverse events (SAEs), and device malfunctions by overall occurrence and imaging modality (DBT and as needed, repeat FFDM) that occur during the study will be collected. No other clinical safety assessments will be performed.

## 6. DESIGN OF RESEARCH STUDY

[figure not shown]
## 6.1. Type of Research Study

### 6.1.1. Study Type

This study (ADAPT-SCR) is an open-label, multi-center, within-subject crossover, randomized, prospective clinical research study, collecting images and associated data from bi-lateral two-view DBT and FFDM exams conducted with GE systems. Study subjects will be asymptomatic adult women aged  $\geq 30$  years undergoing routine screening mammography.

The data from this study will be pooled with data from other subjects who will have been recruited under other GEHC protocols (including ADAPT-BX), for a blinded reader study and analysis described in a separate protocol (ADAPT-BIE). Figure 1 depicts the study design and procedures.

**Figure 1: Study Design and Procedures**

*\*FFDM may be collected prior to enrollment if conducted within 30 days of DBT.*

\*\* Concordant histological and imaging findings for benign lesions or evidence of negative 1-year follow-up will serve as truth for non-cancer.

### 6.1.2. Study Design Details:

Open-Label		Interventions are known to researchers and subjects
Blinded		
Double-Blinded		
Single-site		
Multi-site		Data will be pooled from multiple studies (e.g. ADAPT-SCR & ADAPT-BX) at multiple sites
Randomization Procedure:		Reading order of DBT and FFDM will be random
Not randomized:		
Single arm		
Comparator		Diagnostic accuracy of DBT vs FFDM will be assessed in a separate protocol (ADAPT-BIE)
Parallel		
Crossover		This is a within-subject crossover study
Prospective		Subjects are enrolled and then undergo study procedures

### 6.2. Study Timeframe

The study is expected to begin in the fourth quarter of 2014, and last for approximately two years (24 months) or until the target subject population is enrolled or the Sponsor otherwise indicates in writing that enrollment should be terminated. The end of the study shall be defined as the date the last subject is imaged in the one-year follow-up. Total participation for each subject is expected to be 10-16 months, unless completed early due to truth determination of cancer status. The Investigator shall not begin study until the applicable EC/IRB approval has been obtained.

### 6.3. Controls and Minimization of Bias

The following bias control methods are being employed in this study:

- a. Selection bias in allocating subjects to interventional groups will be limited by attempting to enroll consecutively eligible subjects; subjects may be recalled for further work-up based on positive screening interpretations on either FFDM or DBT.
- b. Spectrum bias will be limited by using a population expected to be representative of the general population at the investigational site, without regard for race or ethnicity.
- c. Interpretation bias will be managed by randomizing the order that DBT and FFDM are read for subjects as these will usually occur during the same visit.

## 7. STUDY SUBJECTS

### 7.1. Number of Subjects

Up to 250 routine screening mammography (Enrollment ceiling per site will be 150 subjects) subjects will be enrolled from two (2) centers in the US. Data will be pooled with other sources to achieve the target number of positive cancer and non-cancer cases required for analysis, as described in Section 10.1.1 Sample Size Justification.

### 7.2. Subject Population

Study subjects will be adult women ( $\geq 30$  years of age) clinically scheduled for routine screening mammography that are asymptomatic at the time of screening.

### 7.3. Protection of Vulnerable Subjects

This study does not intend to enroll vulnerable subject populations.

### 7.4. Procedures for Enrollment

All subjects must satisfy all the inclusion criteria and none of the exclusion criteria defined in the protocol. Subjects must sign and date the informed consent form prior to completing protocol-specific procedures. The Investigator may discuss with the Sponsor any subject who does not strictly meet the inclusion/exclusion criteria but who is thought to be otherwise appropriate for the study; if the Sponsor and Investigator agree that inclusion of the subject would not affect the scientific or ethical aspects of the study, the Sponsor may provide a written exception for the subject. In this case, the details of the exception will be recorded on the case report form (CRF). Each subject will be assigned a randomized order for reading of their DBT and FFDM images such that approximately half of the subjects will have their DBT images interpreted first and the other half will have their FFDM images interpreted first. A subject will be considered enrolled when determined eligible, informed consent is signed, and randomized read order is assigned, whether or not the subject undergoes study procedures.

## 7.5. Inclusion Criteria

Subjects may be included that meet the following criteria:

1. Women aged 30 years or older ( $\geq 30$  years old);
2. Asymptomatic women scheduled for screening mammography or have completed a screening mammogram within the past 30 days;
3. Mammography completed on a GE FFDM system (with CC and MLO views) at the site or another clinical facility;
4. Are able and willing to comply with study procedures;
5. Have signed and dated the informed consent form;
6. Are either surgically sterile or post-menopausal or, if of childbearing potential, the possibility of pregnancy is remote based on a documented negative patient history and, optionally, a negative urine pregnancy test (if subject requests one).

## 7.6. Exclusion Criteria

Subjects must be excluded from participating in this study if they meet any of the following criteria:

1. Have been previously included in this study;
2. Have a history of breast cancer and are in active treatment. However, subjects with a prior lumpectomy ( $\geq 5$  years prior) who receive only routine screening mammography views can be included;
3. Have breasts too large to be adequately positioned on 24 x 31 centimeter (cm) FFDM digital receptor without anatomical cut off during either FFDM or DBT examination;
4. Have participated in (within the prior 30 days), another trial of an investigational product expected to interfere with study procedures or outcomes;
5. Have breast implant(s);
6. Have reconstructed breast(s).

## 7.7. Screening Subjects for Enrollment

Subjects will be recruited from asymptomatic populations undergoing routine screening mammography at each site, in accordance with local EC/IRB recruitment policy. Enrollment decisions will be based on the Investigator's judgment. Final screening will include confirmation that each subject meets all inclusion and no exclusion criteria. All screening will be conducted in

 If prior mammographic examinations were not conducted at the recruiting site, review of those images by the Investigator must confirm that the subject qualified for this study (CC and MLO views present) and access to the images in DICOM digital format by GE must be granted.

 Subjects who had prior imaging on non-GE equipment may be enrolled if they agree to undergo repeat imaging on a GE FFDM system

 Post-Menopausal is defined as documented 12 months of spontaneous amenorrhea.

**Study Title:** Assessment of Diagnostic Accuracy and Performance of Digital Breast Tomosynthesis Compared to Mammography (ADAPT Trial)  
**Study Number:** 124.03-2014-GES-0010  
**Protocol:** 2.0

---

GE Healthcare

compliance with applicable laws, regulations, and standard procedures at the investigational site.

---

 If prior mammographic examinations were not conducted at the recruiting site, review of those images by the Investigator must confirm that the subject qualified for this study (CC and MLO views present) and access to the images in DICOM digital format by GE must be granted.  
 Subjects who had prior imaging on non-GE equipment may be enrolled if they agree to undergo repeat imaging on a GE FFDM system  
 Post-Menopausal is defined as documented 12 months of spontaneous amenorrhea.

## 8. PROCEDURES FOR RESEARCH STUDY

Table 1: Study Schedule of Events for Study Subjects

Variables	Pre – Study Imaging	Study Imaging	Post - Study Imaging
Informed Consent	X		
Entry Criteria	X		
Demographic Information a	X		
Review Relevant Medical/Surgical History	X		
Randomized Read Order Assigned	X		
DBT Imaging		X	
Collection of Prior Screening FFDM Imaging	X		
Screening FFDM Imaging b		X	
Safety Assessments (AE, SAE, device malfunctions) c		X	
Image assessment by site radiologist			X
Histopathology (if applicable)			X

DBT = Digital Breast Tomosynthesis; FFDM = Full-field digital mammography; AE = adverse event; SAE = serious adverse event;

a: Including age, menopausal status and history of surgical breast intervention. b: Only if prior images are not available or were not obtained on a GE FFDM system. c: Device-related AEs and SAEs

### 8.1. Pre-Study Imaging Procedures

All enrolled subjects will undergo the following procedures prior to receiving their study-specific DBT (and, if necessary, FFDM) mammogram(s):

- A notation will be made in the subject's medical chart that the subject is participating in the clinical trial. Additionally, the notation should indicate the subject had her questions answered, read, signed and dated and has been given a copy of the Informed Consent Form (ICF);
- Study entry criteria, demographic information (including age), relevant reproductive medical/surgical history such as oophorectomy, hysterectomy, or other reproductive or breast surgeries (e.g. aspiration, core biopsy, breast reduction, implant removal surgery, or other surgery) and pregnancy/menopausal status will be reviewed;
- A subject number and randomized reading order will be assigned.

There is no special subject preparation required to perform DBT or FFDM screening mammography.

### 8.2. Baseline (Month 0) Digital Breast Tomosynthesis (DBT) and Full Field Digital Mammography (FFDM) Examinations

Study subjects will undergo two-view DBT (both CC and MLO view) of both breasts or of one breast if they have had prior mastectomy. Prior screening images will be collected from each subject's medical record or, if necessary (because prior screening mammography images are not available or were not performed with GE FFDM equipment), a subject may also need to undergo

repeat FFDM; if so, this will be FFDM (both CC and MLO views) performed on the GE FFDM system available at the site and according to the hospital's standard procedure.

DBT and FFDM image acquisition (both CC and MLO views) will be performed within 30 days of each other, regardless if FFDM was performed before or after the subject agreed to participate in the study. Each subject will undergo the following procedures:

- Enter a changing room to prepare for their mammogram;
- Each subject of child-bearing potential will wear a lead apron or have equivalent shielding during the DBT (and, if necessary, FFDM) procedures;
- Undergo DBT (and, if necessary, FFDM) procedure(s);
- Will be monitored for AEs, SAEs from DBT and FFDM (if repeated) to be recorded in the source document and CRF. Device malfunctions shall be sent to the Sponsor as per Section 12.5 - Management of Device Complaints.

Proper equipment checks as noted in the SenoClaire® - GE Breast Tomosynthesis Operators Manual will be performed prior to imaging any subject. All scanning should be performed within the standard range of scan parameters, as per the manufacturer-provided operator's manual(s) for GE FFDM and DBT devices. The scan operator should conduct DBT and FFDM exam according to the standard clinical practice at the site with consideration for:

- Subjects with large breasts, because perspiration under the breast can cause the skin to soften, and become paper-thin;
- Any condition that exists which may cause unusual discomfort or tearing of the skin, which could include telling the subject the importance of correct positioning. The subject should be positioned carefully to avoid any discomfort to abnormalities such as warts, scarring, or skin which is not intact;
- Warmth of the front part of the breast support, which can be warm to the touch, as it contains electronic components that generate heat;
- Positioning the breast properly in the CC position, where it is essential that the breast is lifted away from the chest wall and gently pulled forward, in order to visualize the maximum amount of breast tissue.

### **8.3. Post-Study Imaging Procedures**

The following assessments will be performed:

- DBT and FFDM images will be assessed at the study site in randomized order by one or more MQSA-qualified radiologists, as per institutional standard practice;
- If clinically indicated based on screening imaging results, subjects will undergo institution's standard practice of diagnostic work-up of findings seen, which may include surgical intervention and breast tissue histopathological analysis.

The IDI MammoWorkstation permits 3-D-reconstruction and 2-D-reconstruction (V-Preview). The evaluating radiologist should use the image reconstruction views appropriate for diagnostic evaluation, per his or her medical judgment, and handle diagnostic evaluations in accordance with the standard of care at the investigational site.

### 8.3.1. On-Site Image Interpretation

DBT and FFDM images of all included subjects will be assessed at the study site by one or more MQSA-qualified radiologist(s) on an IDI MammoWorkstation. The 2-D FFDM or 3-D DBT results may result in a recommendation that breast lesions be worked-up by diagnostic evaluation or biopsied.

The results of DBT alone, however, will not be used as a basis to cancel plans for biopsy of any lesion that would be otherwise recommended based on routine mammography with FFDM.

The evaluating radiologist(s) at the site will record for each subject, the following parameters:

- Breast density (as defined by BI-RADS® density categories)
- Finding characteristics, to include breast location, lesion type, depth, quadrant and size. In the case of multiple findings, a maximum of three (3) most suspicious findings will be scored and localized.
- Screening BI-RADS® score (BI-RADS 1, 2, 3, 4, 5), scores of 0 (indeterminate) should be approximated to the closest definition score of 1 to 5 for each breast based on DBT and FFDM separately

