## 1. STUDY SYNOPSIS

**Title of Study:** Assessment of Diagnostic Accuracy and Performance of Digital Breast Tomosynthesis Compared to Mammography (ADAPT Trial)

*ADAPT-SCR: Recruitment Plan for Asymptomatic Women Undergoing Screening Mammography*

**Protocol Number (Study Number):** 124.03-2014-GES-0010

**Investigators and Study Center(s):** Two (2) centers in the United States (US) will collect cases as part of this study protocol.

[name] Beaumont Health System	Address: [name] Telephone: [contact] E-mail: [contact]
[name] Allegheny General Hospital	Address: [name] Telephone: [contact] E-mail: [contact]

**Objective:** The aim of this recruitment plan (ADAPT-SCR) is to collect image and other data on both digital breast tomosynthesis (DBT) and full-field digital mammography (FFDM) from asymptomatic women undergoing screening mammography. These data will be included in a subsequent and prospectively planned pooled analysis described in a separate protocol (ADAPT-BIE) examining superiority of DBT to FFDM for breast cancer diagnosis and other clinical performance measures.

**Study Design:** An open-label, multi-center, accrual study collecting DBT and FFDM screening images from up to 250 asymptomatic women aged  $\geq 30$  years undergoing routine breast cancer screening will be conducted. CC and MLO views from bilateral GE DBT and GE FFDM (conducted before or after enrollment) within a 30 day window will be collected and assessed on-site by qualified radiologist(s) for clinical management purposes. BI-RADS® scores will be recorded. Results of biopsy(ies) and histopathology, including lesion characteristics, will be recorded.

Subjects with negative or benign imaging findings will be followed for approximately one year (10-16 months) by standard of care imaging to determine cancer status. Subjects with negative or benign histological findings will have their images and histopathology reviewed for concordance, per the site's standard procedures. Histologic concordance with imaging or evidence of negative one-year follow-up will be considered truth for non-cancer status. A positive histology result will be considered truth for cancer.

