### 9.3. Reader Training

All study staff assessing images for this study will be qualified radiologists at the investigational site(s), and reads will be performed according to the standard of care at the investigational site. All readers will be trained on the study protocol and recording of data on case report forms (CRFs) prior to reading images. Determinations made by site radiologists based on DBT and FFDM images collected in this study may be included in the subject's regular medical record.

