#### **10.1.3. Subject Disposition and Characteristics**

Subjects enrolled/randomized, imaged, and withdrawn will be summarized overall and by site and imaging modality. Descriptive statistics and summaries will be provided for demographics, medical histories, image acquisition, lesions and findings and BI-RADS® assessments.

Specific subgroups of interest include stratification by the following variables:

- Age;
- Menopausal status; and
- Breast density.

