Randomized Read Order Assigned	X																																																					
DBT Imaging		X																																																				
Collection of Prior Screening	X																																																					
Screening FFDM Imaging b		X																																																				
Safety Assessments (AE, SAE, device malfunctions) c		X																																																				
Image assessment by			X																																																			
Histopathology (if applicable)			X																																																			
17.	Section 8.1. Pre-Study Imaging Procedures	
8.1. Pre-Mammography Study Imaging Procedures
 
All enrolled subjects will undergo the following procedures prior to receiving their study-specific DBT (and, if necessary, FFDM) mammogram(s):
 

• A notation will be made in the subject's medical chart that the subject is participating in the clinical trial. Additionally, the notation should indicate the subject had her questions answered, read, signed and dated and has been given a copy of the Informed Consent Form (ICF);

• Study entry criteria, demographic information (including age), relevant reproductive medical/surgical history such as oophorectomy, hysterectomy, or other reproductive or breast surgeries (e.g. aspiration, core biopsy, breast reduction, implant removal surgery, or other surgery) and pregnancy/menopausal status will be reviewed;

• A subject number and randomized reading order will be assigned.

 
<del>An area also will be allowed on the CRFs for additional notes or comments relevant to the subject's study procedures, to be completed by the Investigator.</del>
 
<del>There is no special subject preparation required to perform DBT or FFDM screening mammography. Subjects undergoing a</del>
	Revised section title for consistency with Table 1 headings.  Clarified procedures relate to study-specific imaging.  Deleted language regarding Investigator comments to reflect approved format of CRFs.  Deleted inconsequential language for the study protocol. Appropriate language presented in the informed consent forms.																																																			

Item	Section	Revision or Clarification	Justification

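### Does recording a site BI-RADS 0 as the nearest score of 1 to 5, with no listed field that keeps the 0, call for a change to the plan?

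*Combined protocol and SAP*

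**What the plan says.** Section 8.3.1 lists three things the site radiologist records: breast density, the characteristics of up to three findings, and a screening BI-RADS score. The scale for that score is 1 to 5, and for an indeterminate read the instruction is that "scores of 0 (indeterminate) should be approximated to the closest definition score of 1 to 5", applied per breast and separately by modality. Section 8.3.2 adds that extra FFDM views and any other imaging after a call-back are recorded.

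The scores appear in three other places. The Study Design paragraph of the synopsis has the images "assessed on-site by qualified radiologist(s) for clinical management purposes. BI-RADS® scores will be recorded". Section 5.3.1, after defining the primary endpoint as the site's diagnosis of cancer status, adds that "DBT and FFDM image sets will be assessed using BI-RADS® scores". Section 10.1.3 sets out the output: "Descriptive statistics and summaries will be provided for demographics, medical histories, image acquisition, lesions and findings and BI-RADS® assessments".

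On data capture, Section 15.3 says the sponsor supplies the case report forms and any completion instructions. Section 9.3 says: "All readers will be trained on the study protocol and recording of data on case report forms (CRFs) prior to reading images". Neither the forms nor the instructions are among the documents. Item 17 of Appendix A mentions an approved form layout, in deleting an area for investigator comments "to reflect approved format of CRFs"; that remark does not concern BI-RADS.

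**The concern.** A BI-RADS 0 is a screening result in its own right: the reader could not settle the question on the images available. Turning it into a 1 to 5 score forces a choice, and the only guide is closeness to a category definition. With two centers and one or more radiologists reading at each, two readers could resolve similar indeterminate images differently. If nothing records that a score began as a 0, the table cannot show how often this happened or in which modality.

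BI-RADS is also mentioned in the primary endpoint text, and a descriptive summary is the only analysis this study produces. At stake would be how faithfully that summary describes the site reads, and whether site scores could be used later, for example to look at site recall by modality.

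**Working it through.** The plan states no figure on this point, and the documents give no frequency for BI-RADS 0. The check is therefore one of tracing where the score goes, then of scale.

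**Where the score goes**

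- *Truth status.* Sections 8.4 and 8.5 settle cancer status by histology, by concordance of benign histology with imaging, by diagnostic work-up, or by follow-up at 10 to 16 months. Neither names the recorded 1 to 5 score as an input.
- *Accrual and success.* Section 10.4 counts subjects and truth data. Section 10.1.1 counts cancer and non-cancer cases. Neither uses BI-RADS.
- *Analysis set.* The Efficacy Population in Section 10.1.2 depends on eligibility, protocol violations and the images, not on a score.
- *Inference.* Section 5.1 states that no hypothesis is tested, and Section 10.1.1 limits this study to a descriptive summary.
- *DBT against FFDM.* The synopsis and Section 10.1.1 assign ROC, sensitivity, specificity and recall analyses to a blinded image evaluation by independent readers (ADAPT-BIE). What passes to it is the images, not the site score.
- *What is left.* The BI-RADS part of the summary in Section 10.1.3.

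**Size of that table**

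Enrollment is up to 250 (Section 7.1). DBT is taken "of both breasts or of one breast if they have had prior mastectomy", and each breast is scored on both modalities.

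- Scores per woman: 2 breasts × 2 modalities = 4 (2 for a woman with one breast).
- Ceiling: 4 × 250 = 1,000, assuming one recorded read per breast and modality. Section 8.3.1 allows more than one radiologist, so several recorded reads per image set would raise it.
- For an assumed share of 0 reads of 5%, 10% or 15%: 1,000 × 0.05 = 50; 1,000 × 0.10 = 100; 1,000 × 0.15 = 150 approximated scores. These shares are illustrations only. The number is zero if the form keeps the issued score or if no 0 is given.

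**What prospective capture would gain**

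Keeping the issued score beside the 1 to 5 score needs four more fields per woman, an amendment with ethics approval (Section 14.3) and reader retraining. Version 2.0 is dated 15 June 2016, and Section 6.2 expects a start in the fourth quarter of 2014 and a duration of about 24 months.

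- Start on 1 October 2014: 20.5 months elapsed, 24 − 20.5 = 3.5 months left.
- Start on 31 December 2014: 17.5 months elapsed, 24 − 17.5 = 6.5 months left.
- Even enrollment over all 24 months: 3.5/24 × 250 ≈ 36 women to 6.5/24 × 250 ≈ 68 women, so at most about 68 × 4 = 272 scores.
- If the 24 months include follow-up of 10 to 16 months: enrollment closes between month 24 − 16 = 8 and month 24 − 10 = 14, before version 2.0, so 0 women.

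The range is 0 to about 68 of 250. Slower accrual than assumed could push it higher, since Section 6.2 gives the duration only as approximate.

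**What retrospective retrieval would gain**

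Section 9.3 says only that "Determinations made by site radiologists based on DBT and FFDM images collected in this study may be included" in the medical record, so the score may not be there. Section 7.5 accepts FFDM done at another facility. For those women the FFDM score on file could be an outside reader's rather than the study site's. Retrieval could thus create a new mixture of scores while trying to remove the first.

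**The case for a change.** The best case for acting is that the descriptive summary is all this study reports, so it should be right. The text has no criterion for when an indeterminate read becomes a 2, a 3 or a 4, and the listed items do not show which scores were affected. Reading the rule as a scoring convention, under which the reader simply never issues a 0, does not remove the point: the reader of the table still cannot see where the convention was used. Section 8.3.2 helps only in part, because call-back imaging is recorded for the woman and not tied to the modality that prompted it.

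This stands as a description of the text. Three things limit it. First, closeness to a category definition is a criterion, though one that rests on the radiologist's judgment; a fixed conversion would override that judgment, and keeping the 0 would not make the approximation more reproducible. Second, Section 10.1.3 promises neither a 0 category nor a recall rate, and site recall by modality is not an objective here. Third, the forms, their instructions and the reader training are where such detail normally sits, and they cannot be inspected. The mention of BI-RADS in Section 5.3.1 adds little, because the endpoint itself is cancer status.

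**Conclusion.** The observation is accurate but no change to the plan is needed. Followed as written, the plan gives sound truth status, accrual counts and images for the later reader study. What remains is missing detail in one descriptive table, covering at most about 1,000 scores, of which an unknown and possibly zero number were approximated. Added fields and an amendment would serve an estimated 0 to about 68 women, and retrieval from records risks bringing in reads that are not the study's.

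Analysts can fill the gap when reporting. A footnote can say that the scale is 1 to 5 and that indeterminate reads were assigned to the closest category. If the form turns out to hold the issued site score, it can be tabulated as well. Section 10.1.5 already provides for additions to the analysis to be described in the Clinical Study Report.

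This conclusion assumes that site scores are used only descriptively and that the blinded evaluation relies on its own readers, as the synopsis states. If site BI-RADS scores were later used to compare recall or accuracy between modalities, the loss of the 0 would matter and the question would have to be reopened.
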